An open label single arm extension study to further evaluate the safety, tolerability and treatment response of GBT440 in patients with Sickle Cell Disease who participated in the Phase 1 Study GBT440-001

Protocol Number: **GBT440-024**

Quintiles Study Number: **BYA73740**

EudraCT Number: **2016-002123-28**

Product: **GBT440**

Indication: **Sickle Cell Disease**

Clinical Phase: **IIa**

Principal Investigator: **[name], FRCP, FFPM**

Sponsor: **Global Blood Therapeutics, Inc.**

Version: **Version 2**

Date: **28 September 2016**

This protocol is the confidential property of Global Blood Therapeutics, Inc, and is intended solely for the guidance of this clinical investigation. This protocol may not be disclosed to parties not associated with the clinical investigation or used for any other purpose without the prior written consent of Global Blood Therapeutics, Inc.

Summary of protocol amendments

Revisions

- Inclusion criteria has been changed from
 - Subjects with SCD who are currently enrolled in the GBT440-001 study, Cohort 15 or 17
 - to:
 - Subjects with SCD who have participated in the GBT440-001 study.
- Dose titration section has been added allowing increase in dose by 300 mg increments every 2 weeks up to maximum of 1500 mg, if in the opinion of the investigator the subject is tolerating the current dose level and might derive further benefit from an increase in dose (e.g. the hemolysis measures have improved but not yet normalized).
- Placebo subjects in Cohort 15 will initiate treatment with GBT440 at 900 mg.
- Removed concomitant medication restrictions for CYP2D6 substrates
- Removed the collection of the SCD severity questionnaire
- Updated clinical experience with GBT440 in Study GBT440-001

Rationale for revisions

- Because of delays in initiating the GBT440-024 study, several subjects from Cohort 17 of GBT440-001 had already completed dosing and were unable to participate. In addition, many subjects from earlier cohorts expressed interest in longer term, open label dosing with GBT440 in GBT440-024. For this reason the inclusion criteria have been expanded to allow enrolment of subjects with SCD who have completed the GBT440-001 study. These individuals will follow the same schedule indicated in the relevant schedule of assessments (SOA) in Section 17.0.
- Dose titration has been added because data from the GBT440-001 study has shown a linear and highly significant relationship between GBT440 blood level and improvement in hemolysis and no plateau effect has been reached. This suggests that subjects may derive greater benefit at higher doses achieving higher haemoglobin occupancy. Furthermore the target for optimal efficacy based on individuals with HbS/Hereditary persistence of fetal haemoglobin is 20-30% haemoglobin occupancy (Ngo 2011) and the preliminary PK data from Cohort 17 showed that the majority of subjects did not maintain haemoglobin occupancy

>20% at 900 mg daily dosing. In addition, no dose limiting toxicities or concerning dose- or exposure related toxicities pose a safety concern with higher doses. At 1500 mg, the predicted C_{max} is 167 $\mu\text{g}/\text{mL}$, which is less than the C_{max} already observed and found to be well-tolerated in healthy volunteers in GBT440-001 294 $\mu\text{g}/\text{mL}$, 900 mg [Cohort 10]). Provided the principal investigator determines that the 600 mg or the 900 mg dose is well tolerated (after at least 28 days of prior dosing), and that the subject may receive further benefit from higher dosing (further improvement in haemoglobin, reticulocyte count or unconjugated bilirubin) the dose may be increased by one capsule (300 mg) every two weeks up to a maximum of 1500 mg.

- Placebo subjects in Cohort 15 will initiate treatment with GBT440 at 900 mg to increase the likelihood of achieving haemoglobin occupancy $\geq 20\%$.
- The concomitant medication restrictions for CYP2D6 has been removed because preliminary data from the clinical drug-drug interaction study, GBT440-017, suggest that GBT440 does not inhibit metoprolol, a CYP2D6 substrate.
- The version of the SCD severity questionnaire used in this study is an older version, the updated, current version will be added to the upcoming Phase 3 study.

3.0 TABULATED PROTOCOL SUMMARY

Name of Sponsor/Company:	Global Blood Therapeutics, Inc.
Name of Finished Product(s):	GBT440 300 mg capsules
Name of Active Ingredient(s):	GBT440
Title of Study:	An open label single arm extension study to further evaluate the safety, tolerability and treatment response of GBT440 in patients with Sickle Cell Disease who participated in the Phase 1 Study GBT440-001.
Principal Investigator:	[name], FRCP, FFPM
Investigational Site:	The BRC Clinical Research Facility, [name] , Guy's Hospital, Guy's and St Thomas's NHS Foundation Trust [name], UK
Clinical Phase:	Phase IIa
Objectives:	
Primary objective To evaluate the safety and tolerability of up to a total of 6 months dosing in subjects with sickle cell disease (SCD) who participated in the GBT440-001 study.
 
Secondary objectives To observe the pharmacokinetics (PK) of GBT440 in plasma and whole blood in subjects with SCD. To characterize the effect on biomarkers of hemolysis in subjects with SCD.
 
Exploratory objectives To obtain data on exploratory markers of sickle cell disease activity. To obtain data on sickle cell disease symptoms.

Methodology:	
This is an open label, single arm study.
 
Up to 16 subjects with SCD who are 1) enrolled in the GBT440-001 study (Cohorts 15 and 17 only) and are in the treatment period or have completed the treatment period within the prior 7 days or 2) have previously completed the GBT440-001 study will be eligible to initiate daily dosing in this study.
 
Subjects continuing directly from the GBT440-001 study will continue to receive the treatment and dose assigned or a lower dose if the dose was reduced in the GBT440-001 study. Placebo subjects will receive active treatment. Subjects who previously completed the GBT440-001 study will receive 900 mg daily. Prior to enrolment into this study the individual subject treatment allocations for eligible subjects from the GBT440-001 will be unblinded and subjects will be assigned to the following treatment groups:

Group 1

Subjects from Cohort 17 in the GBT440-001 study who have received GBT440 900 mg per day for 4 months will continue receiving GBT440 900 mg per day for a further 2 months in this study.

Group 2

Subjects from Cohort 17 in the GBT440-001 study who have received placebo for 4 months will receive GBT440 900 mg per day for 6 months in this study.

Group 3

Subjects from Cohort 15 in the GBT440-001 study who have received GBT440 600 mg per day for two months will continue receiving GBT440 600 mg for a further 4 months in this study or the dose may be increased if the subject has tolerated 600 mg in GBT440-001.

Group 4

Subjects from Cohort 15 in the GBT440-001 study who have received placebo for 2 months will receive GBT440 900 mg per day for 6 months in this study.

Group 5

Subjects from Cohort 7, 11, 12, 14 16 or 17 who received either GBT440 or placebo who are enrolled into this study will receive GBT440 at a dose of 900 mg per day for 6 months.

All Subjects will receive a total of 6 months treatment with GBT440 which will include treatment with GBT440 in the GBT440-001 study for subjects in Cohort 15 or 17. Subjects from Cohort 7, 11, 12, 14, 16 or 17 who received either GBT440 or placebo and are currently off study in GBT440-001 will receive a total of 6 months of treatment with GBT440 in this study..

The dose may be increased by 300 mg increments (1 capsule) every 2 weeks up to maximum of 1500 mg, if in the opinion of the investigator the subject is tolerating the current dose level and might derive further benefit from an increase in dose (e.g. hemolysis measures have improved but not normalized).

A Safety Monitoring Committee (SMC) consisting of the Principal Investigator, Sponsor Medical Monitor, and Independent Safety Physician will have overall responsibility for assessing safety and tolerability. The SMC will review cumulative data at least monthly to determine whether continued dosing may proceed. The responsibilities of the SMC will be described in a separate charter.

Number of Subjects:

Up to 8 SCD subjects from GBT440-001 cohort 17 (900 mg per day), up to 8 SCD subjects from GBT440-001 cohort 15 (600 mg per day), and additional SCD subjects who previously completed GBT440-001 may be enrolled up to a total sample size not exceeding 16 subjects.

Main Criteria for Inclusion:

Subjects with SCD who are currently enrolled in the GBT440-001 study, Cohort 15 or 17.

Subjects with SCD from Cohort 7, 11, 12, 14, 16 or 17 from the GBT440-001 study.

Eligibility may be determined from assessments obtained as part of the GBT440-001 study within 7 days of dosing in this study for subjects in Cohort 15 or 17.

Eligibility must be determined from assessments obtained during baseline visit for subjects who were previously enrolled in Cohorts 7, 11, 12, 14, 16 or 17.

Subjects who if female and of child bearing potential, are using highly effective methods of contraception from study start to 3 months after the last dose of investigational medicinal product (IMP).

Female subjects must continue to have a negative pregnancy test result.

Subjects whose clinical laboratory test results are not clinically relevant and continue to be acceptable to the Investigator.

Subjects who if male are willing to continue to use barrier methods of contraception, from study start to 3 months after the last dose of investigational product.

Test Product, Dose and Route of Administration:

GBT440 300 mg oral capsules for oral administration.

Duration of Treatment:

Subjects will continue dosing until they have received a total of 6 months treatment with GBT440 which includes prior dosing with GBT440 in the GBT440-001 study for subjects enrolled in Cohorts 15 or 17. Subjects from Cohort 7, 11, 12, 14, 16 or 17 who received either GBT440 or placebo will receive a total of 6 months of treatment with GBT440 in this study.

Criteria for Evaluation**Pharmacokinetics:**

Whole blood and plasma levels of GBT440 as indicated in the schedule of assessments (SOA).

Pharmacodynamics:**Haemolysis markers:**

Haemoglobin, unconjugated bilirubin, LDH, absolute and % reticulocyte counts and % dense cells will be measured as indicated in the SOA.

Disease Related Assessments:

Inflammatory markers and exploratory biomarkers related to SCD disease severity will be assessed as indicated in the SOA.

Safety:

The safety evaluation will include blood pressure, pulse rate, body temperature, respiratory rate, ECG parameters, clinical laboratory tests (haematology, serum biochemistry (including erythropoietin), coagulation, urinalysis and urine microscopy) and adverse events.

Statistical Methods**Pharmacokinetic Parameters:**

Whole blood and plasma levels of GBT440 will be listed and summarised using appropriate descriptive statistics by dose and study day.

Where appropriate an estimate of t_{1/2} will be computed and presented in tabular form with appropriate descriptive statistics.

Pharmacodynamic Parameters:

Haemolysis and Disease related assessments will be listed and summarised using appropriate descriptive statistics.

Safety Parameters:

Individual and summary blood pressures, heart rate, body temperature, respiratory rate, ECG parameters and clinical laboratory data (haematology, serum biochemistry and coagulation) will be presented in tabular form with appropriate descriptive statistics. Adverse events will be tabulated and summarized.

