7.0 INVESTIGATIONAL PLAN

7.1 Overall Study Design

This is an open label, single arm study.

Up to 16 subjects with SCD who were enrolled in the GBT440-001 study (Cohorts 7, 11, 12, 14, 15, 16 or 17 will be eligible to participate.. On attendance to the clinic, subjects in Cohorts 15 or 17 will be asked whether they want to be considered for study GBT440-024. If the subject is interested in study GBT440-024 all consent activities will be completed before the samples/procedures for GBT440-024 are collected/Performed. For subjects who were enrolled in Cohorts 7, 11, 12, 14, 16 or 17 who are interested in participating in study GBT440-024, all consent activities will be completed before the samples/procedures for GBT440-024 are collected/Performed. Prior to enrolment into this study the individual subject treatment allocations for eligible subjects from the GBT440-001 (Cohorts 15 or 17) will be unblinded and subjects will be assigned to the following treatment groups:

Group 1

Subjects from Cohort 17 in the GBT440-001 study who have received GBT440 900 mg per day for 4 months will continue receiving GBT440 900 mg per day for a further 2 months in this study.

Group 2

Subjects from Cohort 17 in the GBT440-001 study who have received placebo for 2 months will receive GBT440 900 mg per day for 6 months in this study.

Group 3

Subjects from Cohort 15 in the GBT440-001 study who have received GBT440 600 mg per day for 2 months will continue receiving GBT440 600 mg for a further 4 months in this study or the dose may be increased if the subject has tolerated 600 mg in GBT440-001.

Group 4

Subjects from Cohort 15 in the GBT440-001 study who have received placebo for 2 months will receive GBT440 900 mg per day for 6 months in this study.

Group 5

Subjects from Cohort 7, 11, 12, 14, 16 or 17 who received either GBT440 or placebo will receive a total of continuous 6 months of treatment with GBT440 in this study (GBT440 024) at a dose of 900 mg per day.

Subjects enrolled on this study will be numbered based on the subject number that were assigned in Study GBT440-001 with the addition of 24 to the beginning of the subject number. eg, Subject 17001 in study GBT440-001 will be assigned number 2417-1001 in this study.

Subject numbering in this study will be as follows:

GBT440-001 Cohort	GBT440-001 Subject Number	GBT440-024 Group	GBT440-024 Subject Number
17	17001-17008	1 and 2	2417-1001 to 2417-1008
15	15001-15008	3 and 4	2415-1001 to 2415-1008

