7.2.1 Subject Inclusion Criteria

1. Male or female subjects with HbSS, HbS/β⁰thalassemia, HbS/β⁺thalassemia, or HbSC aged 18 to 60 years inclusive and >50 kg who have enrolled in cohorts 15 or 17 of the GBT440-001 study and will not experience interruption in dosing for greater than 7 days prior to commencing continuation of dosing in this extension study protocol.
2. Male or female subjects who were enrolled in Cohorts 7, 11, 12, 14, 16 or 17 in the GBT440-001 study (and are currently off-study) are eligible to enroll into this study.
3. Subjects who if female and of child bearing potential, agree to continue to use highly effective methods of contraception prior to enrolment in this study and for 3 months after the last dose of IMP.
4. Subjects whose clinical laboratory test results are not clinically relevant and continue to be acceptable to the Investigator at the final visit of the GBT440-001 study for subjects enrolled in Cohort 15 or 17.
5. Subjects who if male are willing to continue to use barrier methods of contraception, prior to enrolment in this study to 3 months after the last dose of IMP.

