7.2.2 Subject Exclusion Criteria

1. Subjects requiring chronic transfusion therapy.
2. Subjects receiving a blood transfusion within 30 days of enrolment in this study.
3. Subjects with alanine aminotransferase (ALT) or aspartate aminotransferase (AST) >5x upper limit of normal reference range (ULN)
4. Subjects with moderate or severe renal dysfunction (calculated modification of diet in renal disease estimated glomerular filtration rate (MDRD eGFR) <60mL/min/1.73 m² appropriately corrected for race and gender).

5. Subjects with any history of congestive heart failure requiring hospitalisation or whose 12 lead ECG prior to enrolment has a confirmed QTcF interval of >450 msec for male subjects or >470 msec for female subjects.
6. Subjects who do not conform to the above inclusion criteria.
7. Female subjects who are pregnant, trying to become pregnant or lactating.
8. Subjects who have a clinically relevant history or presence of respiratory, gastrointestinal, renal, hepatic, haematological, lymphatic, neurological, cardiovascular, psychiatric, musculoskeletal, genitourinary, immunological, dermatological, connective tissue diseases or disorders, or additional risk factors for torsades de pointe (e.g., heart failure, hypokalemia, personal or family history of long QTc interval).
9. Subjects who have a history of relevant atopy.
10. Subjects who have a history of relevant drug hypersensitivity.
11. Subjects who have a history of alcoholism.
12. Subjects who have a history of drug abuse (N.B. occasional recreational cannabis use is not an exclusion).
13. Subjects who consume more than 14 (female subjects) or 21 (male subjects) units of alcohol a week.
14. Subjects who have a significant infection or known inflammatory process on admission to this study.
15. Subjects who have acute gastrointestinal symptoms at the time of admission (e.g. nausea, vomiting, diarrhoea, heartburn).
16. Subjects who have an acute infection such as influenza at the time of admission.
17. Subjects (females of child-bearing potential and males) who do not agree to use contraception (as defined in Section 7.2.3.2).
18. Subjects who are vegans.
19. Subjects who cannot communicate reliably with the Investigator.
20. Subjects who are unlikely to co-operate with the requirements of the study.

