8.6 Method of Assigning Subjects to Treatment Groups

Following confirmation of continued eligibility subjects will be assigned to the following treatment groups:

Group 1

Subjects from Cohort 17 in the GBT440-001 study who have received GBT440 900 mg per day for 4 months will continue receiving GBT440 900 mg per day for a further 2 months in this study.

Group 2

Subjects from Cohort 17 in the GBT440-001 study who have received placebo for 4 months will receive GBT440 900 mg per day for 6 months in this study.

Group 3

Subjects from Cohort 15 in the GBT440-001 study who have received GBT440 600 mg per day for 2 months will continue receiving GBT440 600 mg for a further 4 months in this study or the dose may be increased if the subject has tolerated 600 mg in GBT440-001.

Group 4

Subjects from Cohort 15 in the GBT440-001 study who have received placebo for 2 months will receive GBT440 900mg per day for 6 months in this study.

Group 5

Subjects from Cohort 7, 11, 12, 14, 16 or 17 who received either GBT440 or placebo who are enrolled into this study will receive GBT440 at a dose of 900 mg per day for a total of 6 months in this study.

All Subjects will receive a total of 6 months treatment with GBT440 which will include treatment with GBT440 in the GBT440-001 study for subjects in Cohort 15 or 17.

Subjects from Cohort 7, 11, 12, 14, 16 or 17 who received either GBT440 or placebo will receive a total of 6 months of treatment with GBT440 in this study.

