Day number	Last treatment day GBT440-001 (+6 days) Cohorts 15 and 17	Baseline for Cohort 7,11,12,14, 16 or 17 (within 7 days of Day 1)	a											
Dense cells	X ^h	X			X		X	X	X	X	X			X
Carboxyhaemoglobin	X ^h	X						X			X			X
HbA1c	X	X						X			X			X
NT-proBNP	X ^h	X						X			X			X
Concomitant medication diary		X	X-----											X

Key

Note: Visit 0 is the last treatment day for subjects in GBT-440-001 (Day 118 for Cohort 17 and Day 60 for Cohort 15)

- a: Enrolment and visit 1 may be combined. On admission to the clinic the subjects will be asked whether they want to be considered for study GBT440-024. If the subject is interested in being enrolled on study GBT440-024 all consent activities will be completed before the samples/procedures for GBT440-001 or GBT440-024 are collected/Performed. Visit 0 (enrolment visit) is the last day of treatment in GBT440-001, which can be 6 days before Visit 1. If the last day of treatment in GBT440-001 (Day 118 or Day 60 for Cohort 17 and Cohort 15) – the enrolment visit is not being repeated as standalone visit.
- b: Complete physical examination on enrolment, a limited physical examination on all other days. Directed physical examinations will be performed as required.
- c: 12 lead ECG (single) will be performed within 30 minutes prior to dose
- d: GBT440 900mg(three capsules) for Group 2 and GBT 440 600mg (2 capsules) for Group 4 and GBT440 900 mg (3 capsules) for Group 5 will be administered daily in the morning. On days when PK samples are drawn GBT 440 should be administered after an overnight fast.
- During the dosing period, subjects will be contacted every week in between outpatient visits to confirm GBT440 administration and subject well being.
- e: Additional samples will be collected if clinically indicated
- f: PK samples will be drawn pre dose. If the dose is increased to 1500 mg, please collect the following timepoints: pre dose, then 1-4 hours, 6-8 hours and 24 hours post dose on study visit days of Day 15 (±3 days), Day 60 (±3 days) and Days 90 (±3 days) of receiving 1500 mg.
- h: Can be omitted if measurements were collected in the past 7 days as part of the GBT440-001 study.

Table 6 Schedule of Assessments Group 3

Group 3: Subjects from Cohort 15 in the GBT440-001 study who have received GBT440 600 mg per day for 2 months will continue receiving GBT440 600 mg per day for a further 4 months (the dose may be increased if the subject tolerated 600 mg in GBT440-001).

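### Group 5 starts at 900 mg per day with no provision for a dose reduced in GBT440-001, although subjects continuing directly keep their reduction

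*Combined protocol and SAP*

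**What the plan says.** The synopsis (Section 3.0, Methodology) sets two start-dose rules.

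- Subjects continuing directly from GBT440-001 "will continue to receive the treatment and dose assigned or a lower dose if the dose was reduced in the GBT440-001 study".
- For the rest: "Subjects who previously completed the GBT440-001 study will receive 900 mg daily".

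The second rule becomes Group 5, which takes subjects from Cohorts 7, 11, 12, 14, 16 or 17, whether they had GBT440 or placebo. Section 7.1 gives them six months "of treatment with GBT440 in this study (GBT440 024) at a dose of 900 mg per day". Section 8.6 says that those "who are enrolled into this study will receive GBT440 at a dose of 900 mg per day for a total of 6 months". Footnote d of Table 5 (Section 17.0) has "GBT440 900 mg (3 capsules) for Group 5 will be administered daily in the morning". None of these places mentions an earlier reduction.

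Inclusion criterion 1 (Section 7.2.1) covers Cohort 15 and 17 subjects who "will not experience interruption in dosing for greater than 7 days". The synopsis uses the same 7 days. Criterion 2 says that subjects from the listed cohorts "in the GBT440-001 study (and are currently off-study) are eligible to enroll into this study".

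The lower-dose clause stands only in the synopsis. Sections 7.1 and 8.6 do not repeat it, even for Groups 1 and 3, to whom it applies.

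**The concern.** Two subjects with the same tolerability history can be given different start doses. Take two Cohort 17 subjects, both reduced from 900 mg. One rolls over within 7 days and keeps the lower dose. The other has a longer gap, falls into Group 5 and is assigned 900 mg. Section 5.3 explains that several Cohort 17 subjects missed the direct route because this study started late, which has nothing to do with how they tolerated the drug.

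The primary objective is safety and tolerability. Returning a subject to a dose already found too high, without a recorded decision that this is safe, is an avoidable risk to that subject. It would also add to the tolerability data an event that the subject's own history could have predicted.

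**Working it through.** There is no planned statistic to reproduce: Section 12.1 says that the sample size has no statistical basis. The check is a reading of every place that could set or alter the Day 1 dose.

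**Step 1. Who is a direct continuer?** The term is not formally defined. The same synopsis paragraph describes Cohort 15 and 17 subjects still on treatment or finished within the prior 7 days, and criterion 1 uses the same limit. On that reading, a Cohort 17 subject with a longer gap is in Group 5.

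**Step 2. Does anything else carry a prior reduction into Day 1?**

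- *Inclusion criterion 2* asks only for past enrolment in a listed cohort and being off-study. The synopsis speaks of completing GBT440-001, so on the criterion's wording a subject who stopped early could also enter at 900 mg.
- *Exclusion criteria (7.2.2).* Criterion 10, "Subjects who have a history of relevant drug hypersensitivity", criterion 8 (clinically relevant organ-system history, including gastrointestinal) and criterion 15 (acute gastrointestinal symptoms at admission) could keep some subjects out. None names a dose reduction, and none sets a lower dose for a subject who enters.
- *Section 8.3* permits reduction, suspension or discontinuation for events in this study. It acts after dosing has begun.
- *Section 8.2* stops dosing at Hb above 12.8 g/dL, with a possible restart at a lower dose. It also acts after dosing has begun.
- *Section 15.2* wants instructions followed exactly. It does foresee a deviation for a subject's well-being, with the sponsor informed, but a lower start would then be a deviation rather than a planned dose.

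**Step 3. Where would 900 mg stand against the dose that was reduced?** Assigned doses are from Section 5.2.1.

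| Cohort | GBT440 dose in GBT440-001 | 900 mg per day is |
|---|---|---|
| 7 | single dose of 1000 mg | no daily dose to reduce |
| 11 | 700 mg/day | above |
| 12 | 500 mg/day | above |
| 14 | 500 mg twice a day (2 × 500 = 1000 mg/day) | below |
| 16 | 700 mg/day | above |
| 17 | 900 mg/day | equal |

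So a reduced subject from Cohorts 11, 12, 16 or 17 would restart at or above the dose that was reduced. For Cohort 14 the documents do not settle it: 900 mg is below the assigned 1000 mg but could still exceed the level the subject was reduced to.

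**Step 4. How many subjects?** Section 5.2.1 reports no dose reductions. Enrolment is capped at 16, so the number affected lies between 0 and 16. One subject in a full study is 1/16 = 6.25% of the safety population.

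**The case against.** The strongest reply is that no affected subject is shown. Section 5.2.1 describes mostly Grade 1 events, a few possibly related Grade 2 events and no drug-related serious or severe events. Section 5.3.1 says that 900 mg for 90 days and 1000 mg for 28 days were well tolerated. This stands, and it limits the size of the point. It does not show that there were no reductions: in this study Section 8.3 allows one for a mild event lasting 72 hours, and the GBT440-001 reduction rules are not given.

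A second reply is that the clause for direct continuers may express continuity of dosing, not a principle. Within this study, Section 8.3 defaults to resuming the original dose once an event has resolved, unless the investigator judges that unsafe. A reader might infer that the protocol accepts that every earlier reduction must be kept; Section 8.3 does not support that. What stands is narrower. Section 8.3 puts a safety judgement before the return to full dose, and Group 5 has none.

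Third, Section 5.3.1 gives a reason not to go lower: most Cohort 17 subjects did not hold haemoglobin occupancy above 20% at 900 mg. That supports 900 mg as the usual start. It does not explain the split, because the same target applies to direct continuers, who keep their reduction.

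Fourth, there are safeguards: a new baseline visit, weekly contact, a Day 15 visit with laboratory tests, and review by the Safety Monitoring Committee at least monthly. These are real. A reader might infer that a Group 5 subject could go lower only after a new adverse event; the haemoglobin rule in Section 8.2 is a separate route. But the baseline visit is off drug, and the other measures work only after 900 mg has been started.

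**Conclusion.** The concern holds as a gap in the start-dose rule. Group 5 is assigned 900 mg per day on Day 1, and nothing in the protocol carries a GBT440-001 reduction into that dose. Subjects continuing directly have such a provision, in the synopsis only. The conclusion rests on the 7-day reading of direct continuation in Step 1.

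Its practical size is unknown and may be 0. A reader might infer that some Group 5 subjects are known to have been reduced, or try to put a probability on it. The documents give no reduction rate, so any such figure would rest on an assumption with no anchor. A reader might also divide 900 mg by the assigned cohort doses and call the result the size of the problem. Those ratios apply to every active subject in the cohort, reduced or not, so they describe the choice of 900 mg as the start dose and not this gap. Only the ordering in Step 3 can be claimed.

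The change is worth making in the next amendment because it protects subjects at little cost. It is not evidence that anyone has been harmed.

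**What to change.** In the synopsis sentence on previous completers, in Group 5 of Sections 3.0, 7.1 and 8.6, and in footnote d of Table 5, write:

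> 900 mg per day, or a lower dose (in 300 mg capsules) if the subject's GBT440 dose was reduced in GBT440-001 for a drug-related reason, unless the investigator and Medical Monitor document before Day 1 that 900 mg can be given safely.

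The last part leaves room for causes that have resolved, in line with Section 8.3.

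Three alignments are needed for this to work:

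- Repeat the existing lower-dose clause for Groups 1 and 3 in Sections 7.1 and 8.6.
- Extend the unblinding text in Section 7.1, now limited to Cohorts 15 or 17, to all Group 5 cohorts. The synopsis already has no such limit, and without unblinding a reduction on placebo cannot be told from one on GBT440.
- Let Section 8.2.1 apply titration from the subject's current dose after at least 28 tolerated days. It now names 600 mg only for Cohort 15 and 900 mg for the others, so a Group 5 subject started lower would have no titration rule.

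The cost is the amendment text and a check of each Group 5 subject's GBT440-001 dosing record at baseline, with no added visits, samples or subjects. A few subjects may contribute less data at 900 mg; Section 12.3 already summarises drug levels by dose.
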